#### **8.2.4.3. Management of Hyperglycemia**

Hyperglycemia is defined as the following:

- Fasting blood glucose  $\geq 270$  mg/dL (15.0 mmol/L) using glucometer (or central laboratory).

After randomization, participants noted to have a fasting blood glucose value (during home glucose monitoring) meeting the above definition of hyperglycemia must be instructed to repeat the measurement the next day (following at least an 8- (preferably 10-) hour fast, except water). If the second measurement also meets the above definition, participants must be asked to return to the site a day later (following at least an 8- (preferably 10-) hour fast, except water) and have blood collected for fasting plasma glucose (and shipped to the central laboratory for analysis).

The investigator should determine if the participant collected the samples after an adequate fasting period; and if the participant is following recommended dietary guidelines. Proper dietary and collected procedures should be reinforced with the participant.

If the results from the central laboratory confirm the readings using glucometer, the participant should receive glycemic rescue medication at the discretion of the investigator (see [Section 6.5.3](#)).

#### **8.2.5. Clinical Safety Laboratory Assessments**

See [Appendix 2](#) for the list of clinical safety laboratory tests to be performed and the [SoA](#) for the timing and frequency.

The investigator must review the laboratory report, document this review, and record any clinically relevant changes occurring during the study in the AE section of the CRF.

Clinically significant abnormal laboratory findings are those which are not associated with the underlying disease, unless judged by the investigator to be more severe than expected for the participant's condition.

All laboratory tests with values considered clinically significantly abnormal during participation in the study or within 28 to 35 days after the last dose of study intervention should be repeated until the values return to normal or baseline or are no longer considered clinically significant by the investigator or medical monitor.

If such values do not return to normal/baseline within a period of time judged reasonable by the investigator, the etiology should be identified and the sponsor notified.

All protocol-required laboratory assessments, as defined in [Appendix 2](#), must be conducted in accordance with the laboratory manual and the [SoA](#).

If laboratory values from non-protocol-specified laboratory assessments performed at the institution's local laboratory require a change in participant management or are considered clinically significant by the investigator (eg, SAE or AE or dose modification), then the results must be recorded in the CRF.

### **8.2.6. Pregnancy Testing**

Pregnancy tests will be both urine and serum tests, and must have a sensitivity of at least 25 mIU/mL. Serum pregnancy test will be required for eCRF collection. Urine pregnancy test will be used for site reference until serum pregnancy result becomes available.

Pregnancy tests will be performed in all females at the times listed in the [SoA](#). Following a negative pregnancy test result at screening, appropriate contraception must be commenced and a second negative pregnancy test result will be required at the baseline visit prior the participant's receiving the IP. Pregnancy tests will also be done whenever one menstrual cycle is missed during the active treatment period (or when potential pregnancy is otherwise suspected) and at the end of the study. Pregnancy tests may also be repeated if requested by institutional review boards (IRBs)/ethics committees (ECs) or if required by local regulations.

### **8.2.7. Mental Health Questionnaires**

#### **8.2.7.1. Columbia Suicide Severity Rating Scale (C-SSRS)**

The C-SSRS is an interview-based rating scale to systematically assess suicidal ideation and suicidal behavior. The "baseline/screening" version of the C-SSRS will be administered at V1. The "since last visit" version of the C-SSRS will be administered at the other visits specified in the [SoA](#). The C-SSRS will be administered by study site staff who have completed training in its administration. Participants who respond "yes" to questions 4 or 5 (indicating suicidal ideation), or to any suicidal behavioral question on the C-SSRS at V1, V2 or V3 will not be permitted in the study.

##### **8.2.7.1.1. Rater Qualifications**

For specific rating assessments, only qualified raters will be allowed to evaluate and/or rate participants in this study. The minimum qualifications a rater must meet will be outlined in a guidance document provided to each participating site. The level of experience with the target population (or equivalent), specific scale experience (or equivalent), and certification required (if applicable) will be listed and used to determine whether a rater is approved for a given assessment. The rater must become certified to perform selected study assessments before he or she can participate in the conduct of the study. For specifically defined assessments, rater training and standardization exercises may be conducted, and written and signed documentation will be provided by the site for each rater's certification. In return, each site will be provided written and signed documentation outlining each rater's certification for specific study assessments. Recertification may be required at periodic intervals during the study. The raters who administer specific study assessments will be documented in a centralized location and all site staff who administer ratings will be verified in the site study documentation during the conduct of the study.

### **8.2.7.2. Patient Health Questionnaire-9 (PHQ-9)**

The PHQ-9 is a 9 item self-report scale for the assessment of depressive symptoms. The PHQ-9 will be completed by participants and reviewed by site staff at the pre-defined time points outlined in the [SoA](#). A PHQ-9 score of  $\geq 15$  at V1, V2 or V3 indicates clinically significant depression and serves as an exclusion criterion for this study.

### **8.2.7.3. Referral to a Mental Health Professional**

A participant should be referred to a MHP for the following reasons:

- Response of “yes” to question 4 or 5, or on any behavioral question on the C-SSRS;
- A score of  $\geq 15$  on the PHQ-9;
- In the investigator’s judgment a risk assessment or exclusion is required.

A clinically-qualified MHP is a MHP with appropriate training in the assessment of suicide risk, according to local clinical practice standards and regulations, who would normally evaluate the risk for suicidal ideation and behavior in a patient.

Participants who have recurrent suicidal ideation or behavior during the study should be discontinued from the study and treated appropriately. If a study participant endorses a 4 or 5 on the ideation subscale or any behavioral item of the C-SSRS on 2 or more occasions and is confirmed to have active suicidal ideation or behavior on both occasions by a risk assessment conducted by a qualified MHP, then the participant should be discontinued from the study and treated appropriately.

Participants who meet criteria for referral to a MHP, but refuse evaluation and/or treatment by a MHP, must be assessed by the investigator to determine if the participant should be discontinued from dosing or from the study.

## **8.3. Adverse Events and Serious Adverse Events**

The definitions of an AE and an SAE can be found in [Appendix 3](#).

AEs will be reported by the participant (or, when appropriate, by a caregiver, surrogate, or the participant's legally authorized representative).

The investigator and any qualified designees are responsible for detecting, documenting, and recording events that meet the definition of an AE or SAE and remain responsible to pursue and obtain adequate information both to determine the outcome and to assess whether it meets the criteria for classification as an SAE or that caused the participant to discontinue the study intervention (see [Section 7](#)).

In addition, the investigator may be requested by Pfizer Safety to obtain specific follow-up information in an expedited fashion.

### **8.3.1. Time Period and Frequency for Collecting AE and SAE Information**

The time period for actively eliciting and collecting AEs and SAEs (“active collection period”) for each participant begins from the time the participant provides informed consent, which is obtained before the participant’s participation in the study (ie, before undergoing any study-related procedure and/or receiving IP), through and including a minimum of 28 calendar days, except as indicated below, after the last administration of the IP.

For participants who are screen failures, the active collection period ends when screen failure status is determined.

Follow-up by the investigator continues throughout and after the active collection period and until the event or its sequelae resolve or stabilize at a level acceptable to the investigator, and Pfizer concurs with that assessment.

Investigators are not obligated to actively seek AEs or SAEs after conclusion of the study participation. However, if the investigator learns of any SAE, including a death, at any time after a participant has been discharged from the study, and he/she considers the event to be reasonably related to the study intervention or study participation, the investigator must promptly notify the sponsor.

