### 1.2. Schema

### 1.3. Schedule of Activities (SoA)

The SoA table provides an overview of the protocol visits and procedures. Refer to the **STUDY ASSESSMENTS AND PROCEDURES Section 8** of the protocol for detailed information on each procedure and assessment required for compliance with the protocol.

The investigator may schedule visits (unplanned visits) in addition to those listed in the SoA table, to conduct evaluations or assessments required to protect the well-being of the participant.

Protocol Phase (for abbreviations refer to Appendix 10 )	Screen	Run-in	Treatment Phase								Follow-Up		Early Term
Weeks Relative to Dosing on Day 1	-6 to -3	-2	0	2	4	6	8	10	12	13-14	16-17		ET
Days Relative to Dosing on Day 1	-42 to -15	-14±3	1	14±3	28±3	42±3	56±3	70±3	84±3	91-98	112-119 a		--
Visit	V1	V2	V3	V4	V5	V6	V7	V8	V9	V10	V11		ET
Informed consent & demography	x												
Review of eligibility criteria	x	x	x										
Open-ended inquiry for adverse events	x	→	→	→	→	→	→	→	→	→	x	x	
Medical history (update only at V2 and V3)	x	x	x										
Review prior or concomitant treatments	x	x	x	x	x	x	x	x	x	x	x	x	x
Review drug, alcohol/tobacco use	x	x	x	x	x	x	x	x	x	x	x	x	x
Review contraception use (females only)	x	x	x	x	x	x	x	x	x	x	x	x	x
Counseling on diet/exercise guidelines		x											
Dispense glucometer, supplies, diary, and provide training		x											
Review drug diary, glucometer & glucose log b			x	x	x	x	x	x	x	x	x		x
Glucose measurement (fasting, via glucometer, on site)		x	x	x	x	x	x	x	x	x	x		
Mental health questionnaires (C-SSRS, PHQ-9)	x	x	x	x	x	x	x	x	x	x	x		x
Physical examination (height at Screen only) c	x		x							x	x c		x
Body weight (in duplicate)	x	x	x	x	x	x	x	x	x	x	x		x
Supine vital signs assessment	x d	x	x d	x	x	x d	x	x	x	x d	x		x
Supine 12-lead ECG	x		x d	x	x	x d	x	x	x	x d	x		x
Registration in trial (via IRT)	x												
Randomization in trial (via IRT)			x										
Dispensation of IRT		x e	x f	x f	x f	x f	x f	x f	x f				
Witnessed dosing on site of IP (AM dose) – with food	x	x	x	x	x	x	x	x	x				
Compliance via pill count on site of returned IP		x	x	x	x	x	x	x	x				x
Blood Sampling for:													
-Fasting plasma glucose and HbA1c	x	x	x	x	x	x	x	x	x	x	x		x

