-Hematology, chemistry (including eGFR)	x		x	x	x	x	x	x	x	x	x		x

PFIZER CONFIDENTIAL

Protocol Phase (for abbreviations refer to Appendix 10 )	Screen	Run-in	Treatment Phase								Follow-Up		Early Term
			0	2	4	6	8	10	12	13-14	16-17		
Weeks Relative to Dosing on Day 1	-6 to -3	-2	0										ET
Days Relative to Dosing on Day 1	-42 to -15	-14±3	1	14±3	28±3	42±3	56±3	70±3	84±3	91-98	112-119a		--
Visit	V1	V2	V3	V4	V5	V6	V7	V8	V9	V10	V11		ET
-FSH (females only), C-peptide	x												
-Pregnancy test (females only)	x	x	x	x	x	x	x	x	x	x	x		x
Lipids, TSH, free T4, calcitonin, amylase, lipase, TBA, PT/INR/aPTT	x		x		x		x		x	x	x		x
-PF-06882961 PK (pre-dose unless noted)			x g	x	x	x g	x	x	x g				x
-Banked biospecimen: Prep B1.5 & B2.5				x		x			x				x
-Banked biospecimen: Prep D1 (only Day 1) h			x										
Urine Sampling for:													
-Urine drug test	x												
Urinalysis (and microscopy, reflexive)	x		x			x			x	x	x		x
-On-site urine pregnancy test (females only) i	x	x	x	x	x	x	x	x	x	x	x		x

- a. May be a telephone contact, or a visit to the clinic if deemed necessary by the investigator.
- b. For participants with obesity only, the review of the glucometer and glucose log should be completed if participants have signs or symptoms of hypoglycemia. Otherwise, regular glucometer monitoring at home is not required.
- c. Full physical examination performed according to the [SoA](#). A limited physical examination is performed at the follow-up visit and may be performed at non-specified visits if there are findings during the previous exam or new/open AEs, if appropriate and at investigator discretion.
- d. Triplicate assessments (see [Section 8.2.2](#)) will be measured at screening, and pre- and post-dose times at Visit 3, Visit 6 and Visit 9, when both pre-dose and post-dose PK measurements are obtained.
- e. On V2 only, IP reflects single-blind placebo; it is dispensed via IRT.
- f. For V3 through V8, IP is dispensed via IRT and reflects double-blind randomized PF-06882961 or placebo.
- g. PK samples collected pre-dose and within the window approximately 2-6 hours post dose.

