**Table 1. Summary of Treatment-Emergent Adverse Events in C3421002**

	Placebo	PF-06882961 Dose a							
		10 mg BID	15 mg BID b	50 mg BID b	70 mg BID	120 mg BID	120 mg BID ST	120 mg QD	200 mg CR QD
Number of participants evaluable for TEAEs	25	9	9	10	9	9	9	8	10
Number of Participants with TEAEs	17	6	8	10	8	8	9	8	9
Number of Adverse Events	44	8	16	45	31	43	50	35	47

ST= slow titration; CR= controlled release formulation; BID = twice daily; QD = daily.

a. PF-06882961 dose reflects the randomized target dose for the group. Note that some participants in the 50 mg BID, 120 mg BID and 120 mg BID ST groups include subject(s) that, due to tolerability, did not remain on the target dose.

b. Neither the PF-06882961 15 mg BID nor the 50 mg BID dose groups received titration.

The most frequently reported TEAEs were nausea (49.0%), dyspepsia (32.7%), vomiting (26.5%), diarrhea (24.5%), headache (23.5%), and constipation (20.4%). In addition, there was 1 symptomatic hypoglycemic adverse event (AE) that was reported in 1 subject in the 120 mg BID group. This AE was non-fasting, mild in severity and of limited duration.

No deaths occurred in the C3421002 study. Two (2) participants experienced 2 severe TEAEs during the study, 1 of which occurred in the dosing period and was considered treatment related, and the other occurred during the follow-up period and was not considered treatment related. The latter participant experienced 2 non-treatment-related serious adverse events (SAEs), 1 of which occurred in the follow-up period and was a TEAE of severe intensity, and the other SAE occurred outside of the study reporting period.

While there were isolated values for laboratory tests, vital signs and electrocardiogram (ECG) intervals outside of the reference ranges, no clear adverse trends were apparent in these parameters. As has been reported for marketed GLP-1R agonists, increases in heart rate have been observed, with mean increases ranging from 5 to 15 beats per minute (bpm) across doses administered to date, and most heart rate values within the normal range.

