#### **4.4. End of Study Definition**

A participant is considered to have completed the study if he/she has completed all phases of the study, including the follow-up visit (Visit 11), approximately 28 to 35 days post last dose of double-blind investigator product (IP).

The end of the study is defined as the date of the follow-up last visit (Visit 11) of the last participant in the study.

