**Table 2. Titration Schemes**

Week of Study	Arm 1	Arm 2	Arm 3	Arm 4	Arms 6 and 7
1	5 mg BID	10 mg BID	5 mg BID	10 mg BID	10 mg BID
2	10 mg BID	20 mg BID	5 mg BID	10 mg BID	20 mg BID
3	20 mg BID	40 mg BID	10 mg BID	20 mg BID	40 mg BID
4	40 mg BID	60 mg BID	10 mg BID	20 mg BID	60 mg BID
5	60 mg BID	80 mg BID	20 mg BID	40 mg BID	80 mg BID
6	80 mg BID	100 mg BID	20 mg BID	40 mg BID	100 mg BID
7	100 mg BID	120 mg BID	40 mg BID	60 mg BID	120 mg BID
8	120 mg BID	120 mg BID	40 mg BID	60 mg BID	140 mg BID
9	120 mg BID	120 mg BID	60 mg BID	80 mg BID	160 mg BID
10	120 mg BID	120 mg BID	60 mg BID	80 mg BID	180 mg BID
11	120 mg BID	120 mg BID	80 mg BID	80 mg BID	200 mg BID
12	120 mg BID	120 mg BID	80 mg BID	80 mg BID	200 mg BID

Morning dosing will occur with the food at the site at Visit 2 through Visit 9. Participants will be instructed to arrive at the site in the fasted state, bring their IP with them and to delay self-administration of IP and concomitant medications, if appropriate (as described in [Section 5.3.1](#)), on scheduled visit days until they arrive for their outpatient clinic visit.

Participants should be instructed that if they forget to take their morning dose at their usual time, they should take the missed dose as soon as possible (with food) on the day it was missed; however, there must be at least an 8-hour interval between the missed dose and the next dose. If a dose is missed and the interval to the next dose is less than 8 hours, the missed dose should not be administered.

Dosing and administration instructions along with the dosing diary, will be provided to participants to support at-home dosing of IP.

If participants schedule a visit prior to the protocol specified visit day they should be instructed by the investigator or site staff to continue dosing from the blister card they were dispensed previously.

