### **7.2. Participant Discontinuation/Withdrawal From the Study**

A participant may withdraw from the study at any time at his/her own request, or may be withdrawn at any time at the discretion of the investigator for safety, behavioral, compliance, or administrative reasons.

At the time of discontinuing from the study, if possible, an early termination visit should be conducted. See the [SoA](#) for assessments to be collected at the time of early termination and follow-up and for any further evaluations that need to be completed.

The early termination visit applies only to participants who are randomized and then are prematurely withdrawn from the study. Participants should be questioned regarding their reason for withdrawal. The participant will be permanently discontinued both from the study intervention and from the study at that time.

If a participant withdraws from the study, he/she may request destruction of any remaining samples, but data already generated from the samples will continue to be available, and may be used to protect the integrity of existing analyses. The investigator must document any such requests in the site study records.

If the participant withdraws from the study and also withdraws consent (see below) for disclosure of future information, no further evaluations should be performed and no additional data should be collected. The sponsor may retain and continue to use any data collected before such withdrawal of consent.

When a participant withdraws from the study because of an SAE, the SAE must be recorded on the CRF and reported on the Clinical Trial (CT) SAE Report.

Lack of completion of all or any of the withdrawal/early termination procedures will not be viewed as protocol deviations so long as the participant's safety was preserved.

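### The visit schedule does not guarantee the 28 days of post-dose adverse event collection that Protocol 8.3.1 requires, chiefly for participants who withdraw from the study early

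*Protocol*

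**What the plan says.** - **Requirement.** Protocol 8.3.1 has AEs and SAEs actively elicited for each participant from consent "through and including a minimum of 28 calendar days, except as indicated below, after the last administration of the IP". The text below that sentence gives an earlier end for screen failures. It also says: "Investigators are not obligated to actively seek AEs or SAEs after conclusion of the study participation". Section 8.3.5.1 collects pregnancies over the same 28 days.
- **Visit timing.** The SoA row headed "Days Relative to Dosing on Day 1" puts Visit 9 at Day 84±3 and Visit 11 at Days 112-119. Footnote a says of Visit 11: "May be a telephone contact, or a visit to the clinic if deemed necessary by the investigator". Section 4.4 places the same visit about 28 to 35 days after the last double-blind dose.
- **Last dose.** Section 6.1.1 states: "Morning dosing will occur with the food at the site at Visit 2 through Visit 9". SoA footnote f limits dispensing of randomised product to Visits 3 to 8. A completer's last scheduled dose is therefore on the day of Visit 9.
- **Stopping study drug only.** Section 7.1 and the consent paragraph of 7.2 keep these participants in the study and on the visit schedule.
- **Leaving the study.** Section 7.2 asks for an ET visit where this can be done, and then: "The participant will be permanently discontinued both from the study intervention and from the study at that time". It points to the SoA for follow-up, but the SoA has a single ET column with nothing scheduled after it. Section 7.2 adds that missed withdrawal or ET procedures are not deviations as long as safety was preserved.

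**The concern.** The primary endpoint is the incidence and severity of treatment-emergent AEs, reported by arm (Protocol 3 and 9.4.2). SAP 3.5.1 treats an event as treatment emergent if it starts up to 365 days after the last dose. That rule classifies events but adds no collection, so the incidence observed depends on how long each participant was asked.

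If completers are asked for about four weeks after the last dose and early leavers for a few days or not at all, the safety record is thinner for people who left early, some of them perhaps because of the drug. It would also be uneven between arms if withdrawals were uneven. The group includes participants taken out of the study for recurrent suicidal ideation or behaviour (Protocol 8.2.7.3), for whom later contact has obvious safety value. Pregnancies in the 28 days could be missed in the same way.

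**Working it through.** **Inputs.** Required collection: at least 28 days after last dose (8.3.1). Visit 9: Days 81 to 87 (SoA, 84±3). Visit 11: Days 112 to 119 (SoA). Randomised: 140, drop-out 25%, completing 105 (4.1, 9.2). The last dose of a completer is taken as the day of Visit 9; an evening dose that day leaves the calendar-day count unchanged.

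**1. Reproduce the plan's interval.** With Visit 9 on its nominal day, 112 − 84 = 28 and 119 − 84 = 35. This matches the interval in Section 4.4.

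**2. Apply the allowed windows.** Shortest gap: 112 − 87 = 25 days. Longest: 119 − 81 = 38 days. There are 7 × 8 = 56 allowed pairs of days, and 6 give fewer than 28:

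| Visit 9 (last dose) | Visit 11 | Gap in days |
|---|---|---|
| Day 85 | Day 112 | 27 |
| Day 86 | Day 112 | 26 |
| Day 86 | Day 113 | 27 |
| Day 87 | Day 112 | 25 |
| Day 87 | Day 113 | 26 |
| Day 87 | Day 114 | 27 |

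The six pairs are a count of permitted combinations, not a probability.

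**3. Can a site satisfy every passage at once?** Yes. Last dose plus 28 to 35 days is Days 109-116 for a Day 81 dose and Days 115-122 for a Day 87 dose. These overlap the SoA window at Days 112-116 and 115-119, and the doses in between overlap it too.

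**4. Participants who stop drug but stay.** If the last dose is on Day 80 or earlier, Visit 11 falls at least 112 − 80 = 32 days later. No gap arises.

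**5. Participants who leave the study.** The last scheduled AE inquiry is the ET visit. The documents do not say how soon after the last dose that visit falls. For assumed delays of 0, 3, 7 and 14 days, the part of the 28 days with no scheduled contact is 28, 25, 21 and 14 days.

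**6. Ceiling on numbers.** 0.25 × 140 = 35, and 140 − 35 = 105, which agrees with the plan. The documents do not split the 35 by reason or timing. Three groups must come out of it: those lost to follow-up, those who refuse further contact, and those who stopped drug early and left more than 28 days after the last dose. The affected number is therefore unknown and at most about 35.

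**The case against.** The strongest reply is that Section 8.3.1 binds for each participant whatever the visit dates, and that the plan's normal route for intolerance is already safe. Section 7.1 expects a participant with a tolerability problem to stop drug, stay in the study and attend through Visit 11, and the consent paragraph of 7.2 says the same. That stands, and it confines the main point to people who leave the study itself. For them the reply fails: 7.2 treats withdrawal from the study as a separate event, and treats withdrawal of consent as a further step beyond it. So some people could still be telephoned, but no call is scheduled.

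It can also be said that the exception clause in 8.3.1 extends to the later sentence on concluded participation, which would exempt early leavers. The text does not say so. If that is the intention, it should be stated.

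Other safeguards are real. The SoA lists an AE inquiry and pregnancy tests at ET, known events are followed to resolution or stabilisation, and SAEs learned of later are reportable. None of these is active elicitation of new events to day 28.

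The effect on the gastrointestinal analyses is limited. The weekly tables stop at Week 12 (SAP 6.1.1.2.4 and 6.1.1.2.5), and the subset interval ends two days after the last dose (SAP 3.5.1.2). The overall TEAE tables have no such limit.

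A reader might cite the sponsor's earlier 28-day study, C3421002, where one of two severe TEAEs arose after dosing. Protocol 2.2.2.1 says that "the other occurred during the follow-up period and was not considered treatment related". It shows that severe events can arise in that window, not that drug-related ones are being missed.

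**Conclusion.** The 28-day window is required for each participant but is not guaranteed by the schedule, and Sections 8.3.1, 7.2, 4.4 and the SoA need to be reconciled.

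- **Main point.** Participants who withdraw from the study have no scheduled contact after ET. The size is an unknown subset of at most about 35 of 140, on the planned 25% drop-out and after the exclusions in step 6 of the working.
- **Minor point.** For completers the shortfall is 1 to 3 days, and only when Visit 9 is on Days 85-87 and Visit 11 on Days 112-114.

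Three stronger readings are tempting and are not supported. The window is not generally missed: the nominal schedule delivers it, and a date satisfying every passage always exists for completers. Thirty-five participants are not shown to lose follow-up, since that figure is a ceiling. Under-ascertainment in the more demanding titration arms is plausible if withdrawals cluster there, but the documents give no evidence that they will.

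The change is still worth making, because it alters what sites do and completes the record for the primary endpoint.

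**What to change.** 1. **SoA, Visit 11.** For participants who complete treatment, time the visit at 28 to 35 days after the last dose of study drug, as in Section 4.4, and not before day 28. Leave those who stop drug early but stay in the study on the Day 1 schedule, which already gives them more than 28 days.
2. **Section 7.2 and the SoA ET column.** State that every randomised participant who leaves the study early and has not withdrawn consent for contact receives the Visit 11 contact at least 28 days after the last dose, covering AEs, SAEs and pregnancy. Footnote a already allows this by telephone.
3. **Section 8.3.1.** Make clear that the sentence on events after the end of participation does not shorten the 28 days for these participants.

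The cost is wording, one call each for at most about 35 participants, and slightly later close-out for some. For a last dose on Day 87, for example, the Visit 11 window would run from Day 115 to Day 122 instead of Day 112 to Day 119. People who are lost or who refuse contact would still be missing, and their numbers by arm should be reported beside the TEAE tables.
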